3.2.2. Secondary Endpoints

- Change and percentage change from baseline in resting SpO₂ at Days 15 and 28 measured prior to beginning the 6MWT.
- Change and percentage change from baseline in end-of-6MWT SpO₂ at Days 15 and 28.
- Change and percentage change from baseline in lowest SpO₂ value measured during the 6MWT at Days 15 and 28.
- Pharmacokinetic (PK) parameters of GBT440 in plasma and whole blood, including but not limited to maximum concentration (C_{max}), minimum concentration (C_{min}) at steady state in GBT440 treated subjects.

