5.5.2. Oxygen Saturation

During screening and with all scheduled vital sign assessments resting, room air oxygen saturation (SpO₂) will be measured by pulse oximetry (provided by the Sponsor) whilst the subject is seated and resting for at least 5 minutes. Before recording the SpO₂ value in the eCRF the study staff should ensure the measurement is stable, which may require continuous or repeated measurements and ensuring the subject is resting.

SpO₂ will be also be collected at baseline, during and following completion of the 6MWT and cardio-pulmonary exercise testing.

5.5.3. 6-Minute Walk Test (6MWT)

Functional exercise capacity will be evaluated at Baseline and Days 15, 28 and 58 using the 6-minute walk test. The 6MWT will be performed without the subject using supplementary oxygen. Oxygen may be used at any time during the 6MWT, if in the opinion of the Investigator or testing technician it is required for safety reasons. The 6MWT should then be stopped.

The baseline 6MWT performed at screening must be performed within 7 days of the Day 1 visit. If the 6MWT falls outside of the 7-day window, it must be repeated (the repeat may occur at the time of the Day 1 visit prior to any Day 1 visit assessments).

Guidelines developed by the ERS/ATS will be used for conducting the test and interpreting the results ([ATS 2002](#) and [Holland 2014](#)). Instructions for the conduct of the 6MWT will be provided in a separate manual.

The 6MWT should be performed at each scheduled visit at approximately the same time of day (e.g. in the morning) and after spirometry and DL_{CO} assessments (if scheduled on the same Visit day).

As part of the 6MWT, SpO₂, heart rate and the Borg dyspnea scale will be measured at the following time points: prior to starting the test, during the test, at completion of the test, 1 minute and 2 minutes after test completion.

For safety reasons, all patients should be clinically stable prior to performing the 6MWT.

Absolute contraindications to the 6MWT include unstable angina or myocardial infarction during the previous month.

Relative contraindications to participation in the 6MWT include:

- Resting heart rate >120 or <60 beats per minute
- Systolic blood pressure >180 mmHg
- Diastolic blood pressure >100 mmHg

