15.2.4 Clinical Laboratory Results

Clinical laboratory data including serum chemistry, liver function tests, serum hematology, serum erythropoietin, coagulation panel, and urinalysis are collected at specified visits. The quantitative variables will be summarized by study drug and all GT440 with continuous descriptive statistics for each visit in the Safety population. Urinalysis results will be presented only as a subject listing. Change from baseline and the percent change from baseline will also be summarized by study drug and all GBT 440. Units for laboratory results will be converted from reported units to SI units in the SDTM datasets. Reported results and units will be used for the summary tables.

Subject listings of laboratory data will include a separate listing for clinically significant laboratory values in addition to subject listings of all laboratory values. Listings will be presented with reported units and SI units. Pregnancy test results for both serum and urinalysis sampling will be provided in a separate listing.

16. Secondary Analyses of 6-Minute Walk Test

The 6-Minute Walk Test is a multiple period assessment that includes a resting period (first minute before the walking portion), the 6-minute walking period, and a post-walking period that includes results at each minute for 2 minutes upon completion of walking. End of exercise is defined as last SpO₂ immediately at end of 6MWT (not including the post-walking period). Blood pressure is collected at rest

and at each minute post walking. The distance walked (meters) is recorded at the end of the walking period.

Results of the 6-Minute Walk test (6MWT) will be summarized by study drug and all GBT440 at the following visits: Baseline (Screening or repeat at Day 1 if applicable), Day 15, Day 28, and Day 58. The number and percentage of subjects in each treatment group and all GBT 440 who completed the 6MWT, experienced myocardial infarction (MI) or unstable angina in the previous 30 days before the 6MWT, and utilized oxygen during the 6MWT will be summarized. Summary statistics (N, mean, SD, median, min, and max) will be displayed for systolic and diastolic blood pressure collected at rest and at each minute post-walking.

Subject listings will be provided for all 6MWT data collected on the eCRF.

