Summary statistics for resting SpO₂, SpO₂ at end of the 6MWT (last available result) and lowest SpO₂ collected during the 6MWT will be summarized at each visit by study drug and all GBT440 in the Efficacy-Evaluable population. Summary statistics for the change and percent change from baseline to Day 15, Day 28, and Day 58 also will be displayed.

Analysis of covariance models (ANCOVA) will be used to analyze the effect of treatment on the change from baseline and the percent change from baseline for each secondary endpoint with baseline value as a covariate. Least squares (LS) means and SEs will be displayed for the change and percent change from baseline in each treatment group and for all GBT440.

LS means (95% CI) and p-values from the models will be used to make the following comparisons:

- GBT440 600 mg – Placebo
- GBT440-900 mg – Placebo
- GBT440-1500 mg – Placebo
- All GBT 440 – Placebo

17. Exploratory Analyses

17.1 6-Minute Walk Test

Summary statistics for the distance walked (meters) during the 6MWT, time to the first SpO₂ < 88%, and AUC of SpO₂ will be summarized by study drug and all GBT 440, and visit in the Efficacy-Evaluable population. The change and percent change from baseline to Day 15, Day 28, and Day 58 in distance walked also will be summarized and displayed.

The AUC of SpO₂ measurements will be calculated for each subject's data at baseline, Day 15, Day 28, and Day 58. The AUC will be estimated using the trapezoid rule for data collected on the eCRF as follows:

$$AUC = \left\{ \sum_{t=1}^n \frac{1}{2} [(Time_t - Time_{t-1}) \times (SpO2_t + SpO2_{t-1})] \right\}$$

where n is the number of measurements of SpO₂ collected during the 6MWT, t is the elapsed time in minutes (nominal time) and SpO₂ is the measurement of SpO₂ level at the respective timepoint, and Time is the timepoint. If a SpO₂ measurement is missing during the 6MWT, then that timepoint is removed from the calculation, such that the AUC is calculated using the trapezoid rule from the 2 timepoints surrounding the missing SpO₂ measurement.

Additional exploratory endpoints include the change from rest to end of 6MWT and change from rest to lowest SpO₂. Both endpoints will be summarized by study drug and all GBT440.

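### The SAP's rule for end-of-6MWT SpO2 does not exclude a completion reading taken on rescue oxygen, so a rescued walk can be analysed as if it were on room air

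*SAP*

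**What the plan says.** Protocol Section 3.2.2 lists "Change and percentage change from baseline in end-of-6MWT" SpO2 at Days 15 and 28 as a secondary endpoint, and SAP Section 3.2 repeats it.

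On conduct, Protocol Section 5.5.3 states: "The 6MWT will be performed without the subject using supplementary oxygen". It then allows an exception: "Oxygen may be used at any time during the 6MWT", if the investigator or technician judges it necessary on safety grounds. The next sentence is "The 6MWT should then be stopped". SpO2 is measured "prior to starting the test, during the test, at completion of the test, 1 minute and 2 minutes after test completion".

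On analysis, SAP Section 16 defines end of exercise as the last SpO2 "immediately at end of 6MWT (not including the post-walking period"). It then summarises SpO2 "at end of the 6MWT (last available result") and fits ANCOVA models to the change and percent change, with baseline as covariate. The same section says that the number and percentage of subjects who "utilized oxygen during the 6MWT will be summarized". Nothing in the SAP links that count to the SpO2 value used, to the model, or to a sensitivity analysis. SAP Section 10.1 rules out imputation of missing efficacy data, and the table of changes in SAP Section 19 does not address the point.

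**The concern.** The protocol's order is oxygen first, stopping second. In a rescued walk the reading at completion can therefore follow the start of oxygen, and it still belongs to the end of the walk rather than to the post-walking period. Under the SAP rule it becomes the subject's end-of-walk value and is treated as a room-air measurement.

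The endpoint is meant to show whether GBT440 improves saturation on exertion. A reading raised by supplementary oxygen measures something else. The planned groups hold 6 to 9 subjects, so one or two such walks can move a group mean noticeably. The SAP expects oxygen use during the test, since it tabulates it, yet leaves open which reading then counts.

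**Working it through.** The plan gives no power, effect size or SD for this endpoint (SAP Section 7), so there is no figure to reproduce.

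**Planned group sizes** (SAP Section 4, pooled as in Section 10.3): placebo 6+3 = 9; 600 mg 6+3 = 9; 900 mg 6; 1500 mg 9. The total is 33, which agrees with the plan.

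**Step 1. Which readings of a rescued walk are eligible?**

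| Reading | Oxygen status | Eligible under SAP 16? |
|---|---|---|
| During the walk, before oxygen | Room air | Yes, if it is the last one |
| At completion, after oxygen started and the walk stopped | On oxygen | Yes; nothing excludes it |
| 1 and 2 minutes after completion | Probably on oxygen | No |

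The exposure is mainly the middle row, plus any walk continued after oxygen despite the stop rule.

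**Step 2. One subject.** Let *d* be the on-oxygen minus room-air difference, assumed to be 4, 8 or 12 points. Assume a baseline end-of-walk SpO2 of 84.
- Room-air end value 80: true change 80 − 84 = −4. Recorded change −4 + *d* = 0, +4 or +8.
- Room-air end value 78: true change −6. With *d* = 4 the recorded change is −2.

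The sign can flip, but need not.

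**Step 3. Group mean.** The shift from *k* affected subjects among *n* is *k* × *d* / *n*. With *k* = 1:
- *n* = 9: 4/9 = 0.44, 8/9 = 0.89, 12/9 = 1.33 points.
- *n* = 6: 4/6 = 0.67, 8/6 = 1.33, 12/6 = 2.00 points.

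**Step 4. Scale.** The SE of a 9 versus 9 difference is SD × √(2/9). For an assumed SD of change of 3 to 5 points this is 1.41 to 2.36 points. One affected subject in a group of 9 therefore shifts the mean by less than one SE.

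**Step 5. Simulation of the four-group ANCOVA.** There were 4,000 runs per setting. Every input is assumed: mean end-of-walk SpO2 84 at baseline (SD 3), slope of follow-up on baseline 0.6, residual SD 4, and rescue whenever the end value falls below 80. Every rescued follow-up walk is read on oxygen and no baseline walk is. Results for 1500 mg minus placebo with a true effect of 3 points in all active groups:

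| *d* | Mean estimate | Runs with p < 0.05 |
|---|---|---|
| 0 (pre-oxygen reading used) | 3.00 | 33% |
| 4 | 2.56 | 31% |
| 8 | 1.97 | 19% |
| 12 | 1.50 | 13% |

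With no true effect, the mean estimate stayed at about 0 and the rejection rate at about 5% for every *d*. Because every rescued follow-up walk is scored on oxygen, the table shows the upper end of the loss for each *d* under these inputs.

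**The case against.** The best reply is that the plan already closes most of the route. Oxygen ends the walk, and SAP Section 16 excludes the post-walking period, where most on-oxygen readings would fall. Its phrase for the last result should be read under its own definition of end of exercise. Detailed conduct is in a manual outside these documents, which may fix when the completion reading is taken. Lowest SpO2, a companion secondary endpoint, is largely protected because the nadir would normally come before oxygen. Oxygen use is tabulated, all 6MWT data are listed, safety is the primary endpoint, and no formal hypotheses are set.

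All of this limits the size of the problem. None of it says that a completion reading on oxygen is excluded.

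A reader might infer more than the documents support:
- *That the worst desaturators will be scored as improved.* The protocol gives no SpO2 trigger for oxygen, and Step 2 shows that a flip is possible but not certain.
- *That everyone enrolled is prone to this.* Entry requires a fall below 88% on the baseline walk, not rescue. Inclusion criterion 9 requires that the investigator judge the subject able to complete the walks unassisted.
- *That follow-up is always compared with a room-air baseline.* The oxygen provision covers the baseline walk too.
- *That the error favours the drug.* More rescue on placebo hides an effect, and more on active flatters the drug. Equal rescue mostly adds noise.
- *That the SpO2 AUC is inflated in the same way.* The AUC in SAP Section 17.1 is not divided by time. At an illustrative 85%, six minutes give 85 × 6 = 510 and a walk stopped at minute 3 gives 85 × 3 = 255. A 10-point rise in the last one-minute reading adds only ½ × 1 × 10 = 5. A stopped walk already scores far lower, and removing readings would shorten it further.

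**Conclusion.** The gap is real but narrow. The stop rule and the post-walking exclusion reduce it without closing it: as written, an on-oxygen completion reading can enter the ANCOVA of a secondary endpoint as a room-air value. One such subject moves a group mean by about 0.4 to 1.3 points (n=9) or 0.7 to 2.0 points (n=6), if oxygen adds 4 to 12 points. That range, the SDs and the simulated rescue threshold are assumptions, and the documents give no rescue frequency. The simulated loss of effect arises because rescue is then more common on placebo. The point does not threaten the primary endpoint. It merits correction because the rule is undefined for an event the SAP expects, the groups are small, and the remedy is cheap.

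**What to change.** In SAP Section 16:
1. Define end-of-6MWT SpO2 at every visit, including baseline, as the last walking-period reading before any oxygen was started.
2. Flag oxygen-assisted and early-stopped walks in the tables and listings. A walk stopped early gives its end value after less exercise, even without oxygen.
3. Add a sensitivity analysis with the as-recorded completion value.
4. Add a second one for walks where the eCRF cannot establish whether the reading came before or after oxygen, using the lowest reading of that walk. Keep this out of the main analysis, because it would make the endpoint identical to lowest SpO2 for those subjects and sits awkwardly with the no-imputation rule.

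Confirm whether the eCRF records the start of oxygen relative to each reading; SAP Section 19 notes that SpO2 was not collected in seconds. Settle the rule in advance, since SAP Section 6.3 leaves the sponsor and CRO statistician unblinded in Part B. No change to the AUC is proposed, and nothing changes in the conduct of the test.

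The cost is a few lines of SAP text and some programming. The downsides are that some rescued walks get an earlier or less favourable end value, and that the order may be unrecoverable for some.

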In Part A, two unblinded interim analyses of the primary and secondary endpoints are planned: i) when approximately 9 subjects have completed their Day 28 study visit and ii) when approximately 18 subjects have completed their Day 15 study visit.

A Safety Monitoring Committee (SMC) is planned to review all safety data on an ongoing basis throughout the study (refer to Protocol Section 10.1). If the SMC does not identify any clinically

significant safety concerns in Part A, following review of data from approximately 18 subjects who have completed Day 15, the Sponsor will initiate Part B of the study, and randomize up to an additional 15 subjects to the three study treatment arms to better characterize the safety, tolerability, and potential treatment response of GBT440 in subjects with IPF.

In the eventuality that one treatment arm is discontinued, subjects may be randomized 1:1 to the remaining study drug treatment group or placebo. Therefore, the trial size is approximately 33 subjects.

The end of the study is defined as the date when the last subject completes the last visit, which is expected to occur approximately 58 days after the last subject is randomized.

5. Schedule of Visits and Assessments

The schedule of visits and assessments and PK sampling timepoints are provided below.

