6.1 Method of Assigning Subjects to Treatment Groups

Subject randomization will be carried out centrally through an IxRS. Eligible subjects in Part A will be randomized 1:1:1 to receive 900 mg GBT440, 600 mg GBT440, or Placebo. Eligible subjects in Part B will be randomized 3:1:1 to receive 1500 mg GBT440, 600 mg GBT440, or placebo respectively.

The randomization will be stratified by background IPF therapy (pirfenidone/nintedanib or no pirfenidone/nintedanib) use at the time of entry into the study.

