10.3 Data Analysis Conventions

Analyses for SMC meetings, interim analyses, and final data analysis will be performed by Statistics & Data Corporation (SDC). The final data analyses will be performed after Part B of the study is completed and the database has been locked. Data from Parts A and B of the study will be pooled across the common treatment arms (GBT440 600 mg and placebo arms). Statistical programming and analyses will be performed using SAS® Version 9.4 or higher. All study data will be listed by subject, study drug,

and visit (as applicable) based on randomized and treated subjects unless otherwise specified. Summary statistics will be presented by treatment group including all GBT440, and will include a total column where appropriate.

Study visits will be referred to in all tables and listings as the visit name corresponding to the planned study visit.

Summaries for continuous and ordinal variables will include the number of observations (n), arithmetic mean, standard deviation (SD), median, minimum, and maximum). Minima and maxima will be reported with the same precision as the raw values; means and medians will be presented to one additional decimal place than reported in the raw values. Standard deviations will be presented to two additional decimal places than reported in the raw values. Summaries for discrete variables will include frequency counts and percentages. All percentages will be rounded to one decimal place (i.e., XX.X%).

All statistical tests will be two-sided with a significance level of 0.05 ($\alpha = 0.05$) unless otherwise specified. Confidence intervals (CI) for differences between treatment groups will be two-sided at 95% confidence. All p values will be rounded to four decimal places; p-values less than 0.0001 will be presented as “<0.0001”; p-values greater than 0.9999 will be presented as “>0.9999”.

All summary tables will be supported with subject listings.

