ANCOVA models will be used to analyze the effect of treatment on the change from baseline for each exploratory endpoint with baseline value as a covariate. Least squares (LS) means and SEs will be displayed for the change from baseline in each treatment group and for all GBT440. Similar ANCOVA models will be constructed for percent change from baseline for AUC and distance walked.

LS means (95% CI) and p-values from the models will be used to make the following comparisons:

- GBT440 600 mg – Placebo
- GBT440-900 mg – Placebo
- GBT440-1500 mg – Placebo
- All GBT 440 – Placebo

All exploratory efficacy data will be provided in subject listings.

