17.6 A Tool to Assess Quality of Life (ATAQ)

For Part B of the study only, the ATAQ questionnaires (ATAQ Symptoms and ATAQ Impacts) will be self-administered at Baseline (Day 1), Day 8, Day 15, Day 28, Day 45, and Day 58 to assess subjects' disease symptoms across three domains (dyspnea, cough, and energy level), impact on quality of life across 4 domains (dyspnea, cough, energy level, and global impact), and a set of questions pertaining to oxygen use.

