17.6.3 Analysis of ATAQ Data

Summary statistics for each ATAQ domain will be displayed by study drug and all GBT440, and by visit for the Efficacy-Evaluable population. The change from baseline to each post-baseline visit also will be summarized.

ANCOVA models will be used to analyze the effect of treatment on the change from baseline with baseline value as a covariate. Least squares (LS) means and SEs will be displayed for the change from baseline in each treatment group and for all GBT440.

LS means (95% CI) and p-values from the models will be used to make the following comparisons:

- GBT440 600 mg – Placebo
- GBT440-900 mg – Placebo
- GBT440-1500 mg – Placebo
- All GBT 440 – Placebo

Responses to questions regarding supplemental oxygen use will be summarized with the number and percentage of subjects in each treatment group and for all GBT440 at each visit. Flow rates of oxygen during sleep, during physical activity, and during rest also be summarized with continuous descriptive statistics if at least 2 subjects in each treatment group are on supplemental oxygen. The change from baseline to each post-baseline visit in flow rates will be included as applicable.

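### Placebo is pooled across two sequential randomisations with no Part term, so six of the nine placebo subjects compared with 1500 mg are non-concurrent

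*SAP*

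**What the plan says.** SAP section 4 starts Part B after the safety committee has reviewed about 18 Part A subjects at Day 15. If no safety concern is found, "the Sponsor will initiate Part B of the study, and randomize up to an additional 15 subjects". Part A randomises 1:1:1 to 900 mg, 600 mg and placebo. SAP 6.1 then states: "Eligible subjects in Part B will be randomized 3:1:1 to receive 1500 mg GBT440, 600 mg GBT440, or placebo respectively". SAP 6.3 has the two assignment lists produced by different statisticians.

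SAP 10.3 sets the pooling rule: "Data from Parts A and B of the study will be pooled across the common treatment arms (GBT440 600 mg and placebo arms". Protocol section 11 has the same rule.

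The section 16 ANCOVA takes treatment as the effect and analyses change and "percent change from baseline for each secondary endpoint with baseline value as a covariate". Section 17.1 does the same for "change from baseline for each exploratory endpoint with baseline value as a covariate". Sections 17.2 to 17.6 and 17.8 repeat this form, and 17.7 (CPET) uses the Day 2 value as the covariate. Each section lists 600 mg, 900 mg, 1500 mg and All GBT440, each minus placebo, with 95% CIs and p-values. No Part term, Part-specific comparison or sensitivity analysis by Part appears, and section 19 adds none.

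Two related points:

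- SAP 17.6 collects one instrument in Part B only: "For Part B of the study only, the ATAQ questionnaires". Section 17.6.3 nevertheless lists "GBT440-900 mg – Placebo".
- SAP 6.1 says: "The randomization will be stratified by background IPF therapy (pirfenidone/nintedanib or no pirfenidone/nintedanib) use at the time of entry into the study". That stratum is in none of the models.

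**The concern.** Randomisation protects comparisons within a Part, not across Parts. Part A placebo subjects had no chance of receiving 1500 mg, and Part B placebo subjects had no chance of receiving 900 mg. When placebo is pooled without a Part term, any difference between Parts in change from baseline that is not due to drug enters the contrasts whose arms have different Part splits. The Parts follow one another in time. They also differ in sponsor and CRO-statistician blinding and in daily capsule count (three versus five).

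What is at stake is the dose-response reading. Protocol 1.5.3 justifies adding 1500 mg partly by expecting oxygen saturation to rise with dose, so readers will set the 900 mg and 1500 mg estimates side by side. A Part shift biases those two estimates in opposite directions, so it could create or hide the expected pattern.

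**Working it through.** **Inputs (SAP sections 4 and 7).** Part A has 900 mg 6, 600 mg 6, placebo 6. Part B has 1500 mg 9, 600 mg 3, placebo 3. The ratios reproduce these: 18/3 = 6; 15 × 3/5 = 9; 15 × 1/5 = 3. The total is 18 + 15 = 33, as the SAP states. The documents give no SD, effect size or Part difference, so results are in residual SDs. D is an assumed Part B minus Part A difference in mean change, apart from drug.

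**Non-concurrent share.** Pooled placebo is 6 + 3 = 9. For 1500 mg, 6/9 = 67% are non-concurrent; for 900 mg, 3/9 = 33%.

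**Bias without a Part term.** Bias = D × (share of the dose arm in Part B − share of placebo in Part B). The placebo share is 3/9.

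- 1500 mg: (1 − 1/3)D = +0.67D
- 900 mg: (0 − 1/3)D = −0.33D
- 600 mg: (3/9 − 3/9)D = 0
- All GBT440 weighted by subjects: (12/24 − 1/3)D = +0.17D
- All GBT440 with equal dose weights: ((1/3 + 0 + 1)/3 − 1/3)D = +0.11D (the SAP does not say which weighting applies)

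The apparent 1500 mg versus 900 mg difference therefore absorbs 0.67D + 0.33D = D.

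**Precision.** Without Part, the variance is 1/n1 + 1/n2. With Part, D is estimated from the two arms present in both Parts. Each within-arm difference has variance 1/3 + 1/6 = 1/2, and their mean has variance 1/4. Each contrast's variance then rises by (bias weight)² × 1/4.

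| Contrast with placebo | SE, no Part | SE, Part fitted | SE, concurrent placebo only |
|---|---|---|---|
| 1500 mg | √(1/9 + 1/9) = 0.471 | √(0.222 + 0.111) = 0.577 | √(1/9 + 1/3) = 0.667 |
| 900 mg | √(1/6 + 1/9) = 0.527 | √(0.278 + 0.028) = 0.553 | √(1/6 + 1/6) = 0.577 |
| 600 mg | 0.471 | 0.471 | not needed |

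For 1500 mg the 95% CI half-widths are 0.97, 1.18 and 1.47 SD, counting one df for baseline (28, 27 and 11 error df).

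**Mean squared error.** For 1500 mg, 0.222 + 0.444D² = 0.333 gives |D| = 0.5. The same crossover holds for every biased contrast, because (weight × D)² = weight² × 1/4.

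**Nominal two-sided 5% error with no drug effect.** Simulated normal data, 100,000 sets per D without a baseline covariate and 20,000 with one:

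| D | 1500 mg | 1500 mg, baseline fitted | 900 mg |
|---|---|---|---|
| 0 | 5.0% | 5.2% | 5.0% |
| 0.25 | 6.3% | 6.3% | 5.2% |
| 0.5 | 10.0% | 9.5% | 5.8% |
| 1 | 23.7% | 22.9% | 7.4% |

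With Part in the model, all rates lie between 4.8% and 5.2%. A separate run of 40,000 sets per D gave 5.2%, 6.1%, 10.2% and 23.5% for 1500 mg without a Part term.

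**Additivity.** The Part-by-treatment contrast from the placebo and 600 mg cells has variance 1/2 + 1/2 = 1, so its SE is 1.0 SD. Additivity cannot usefully be tested at this size.

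**ATAQ.** The 15 Part B subjects occupy three arms, so the design has rank 3 for four treatment columns. The 900 mg contrast is not estimable. A Part column leaves the rank at 3.

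**The case against.** The strongest reply is that the harm is hypothetical. The documents show no Part shift. Eligibility criteria are common to both Parts, as is the schedule for every instrument except those restricted to Part B. The baseline covariate already removes much of any difference that acts through initial severity. The highest error rate needs a full residual SD of drift. If |D| is below 0.5, the SAP's unadjusted estimate has the lower mean squared error. The Part term replaces one untestable assumption (no shift) with another (an additive shift), at 22% more SE for 1500 mg. The primary endpoint is unaffected, there are no formal hypotheses, and the SAP specifies neither a 1500 mg versus 900 mg contrast nor a trend test. The ATAQ row and the missing stratum are separate, smaller matters.

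Much of this stands. The bias is conditional on D, and the choice trades bias against variance, which is a reason to keep the unadjusted result alongside. The planned counts may also move. If one Part B 600 mg subject were lost, that contrast would carry (2/8 − 3/9)D = −0.08D. CPET is optional, so the 33-subject SEs and df may not apply to it.

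The structure itself is not answered. The SAP reports CIs and p-values for a comparison that randomisation only partly supports. The non-concurrent share stays a majority unless Part A loses at least 3 of its 6 placebo subjects or Part B placebo reaches at least 6. Section 1 of the SAP allows supplementary analyses but commits to none by Part.

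**Conclusion.** The concern holds and should be fixed. At planned numbers, two thirds of the placebo group for 1500 mg is non-concurrent, and nothing in the models separates a Part effect from a drug effect. That structural conclusion follows directly from the documents.

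The size of any harm rests on D, which is assumed. The bias weights, SEs and error rates also assume the planned arm sizes, and the protection offered by a Part term assumes an additive Part effect. Because the analyses are secondary or exploratory and the p-values nominal, the consequence is for how the 1500 mg, 900 mg and All GBT440 estimates are read. The 600 mg contrast is unaffected while its Part split matches that of placebo.

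For ATAQ, placebo is concurrent and the only fault is a listed contrast that cannot be estimated.

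**What to change.** - For endpoints collected in both Parts, add Part (A/B) as a fixed effect in the section 16 and 17 ANCOVAs, including CPET with its Day 2 covariate. Placebo and 600 mg occur in both Parts, so the term is estimable.
- Add sensitivity analyses of 1500 mg against Part B placebo and 900 mg against Part A placebo, because additivity cannot be checked. The unadjusted pooled result may be shown alongside.
- In section 17.6.3, delete the 900 mg contrast and do not fit Part.
- Separately, add the antifibrotic stratum (yes/no) as a covariate so that the analysis matches the randomisation.

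The cost is SAP wording and analysis work, with no new subjects, visits or data. The SE rises from 0.471 to 0.577 SD for 1500 mg and from 0.527 to 0.553 SD for 900 mg, and is unchanged for 600 mg. Adding the stratum as well gives average SEs of about 0.588, 0.563 and 0.480 SD (1500, 900 and 600 mg), before any variance it explains. Those averages assume 50–80% of subjects on antifibrotics and chance imbalance; balanced strata cost less. Error df go from 28 to 27 with Part and to 26 with both, and the t critical value from 2.048 to 2.052 to 2.056.
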